6.8 Sample Size and Study Power

A feasibility analysis identified more than 10,000 patients in PHD between 2019 and 2021 who were treated surgically with the use of Ethicon Manual Circular Stapler. Among those, approximately 6,000 patients had a left-sided colorectal surgery.

Among approximately 13,000 patients who were treated surgically with Medtronic EEA™ Circular Stapler with DST Series™ Technology, about 6,000 patients had a left-sided colorectal surgery in the PHD.

A similar analysis identified 623 patients in PHD between 2019 and 2021 who underwent surgical procedures where Medtronic EEA™ Circular Stapler with Tri-Staple™ Technology was used. Among those, 526 underwent a left-sided colorectal surgery.

The final sample sizes for the study will vary based on applying the inclusion and exclusion criteria, as well as additional data beyond 2021 being available from PHD.

Power estimates assuming different combinations of relative risk, sample size, and the cumulative incidence of AL in the comparison cohort—Medtronic EEA™ Circular Stapler with Tri-Staple™ Technology— are provided in [Table 2](#)

[Table 2.](#) The calculations assumed one-sided tests at a significance level of 0.025 (or type I error of 0.025). The estimated cumulative incidence of AL among patients who underwent a colorectal surgery with the use of Medtronic EEA™ Circular Stapler with Tri-Staple™ Technology ranges from 2% to 3.5% in the literature.^{8,12}

[Table 2: Power estimation, by relative risk](#)

Relative Risk	AL risk in the comparison cohort	Sample size in the target cohort	Sample size in the comparison cohort	Power
2.5	3%	6,000	500	0.995
2	3%	6,000	500	0.856
1.5	3%	6,000	500	0.324
2.5	2%	6,000	500	0.938
2	2%	6,000	500	0.642
1.5	2%	6,000	500	0.209

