The weighting will be carried out for the comparator group to make it comparable in propensity score to the target group. Two propensity score weighting methods— untrimmed and trimmed— can be used to balance the data to make the target group and the comparison group comparable on the measured confounders. The choice among the methods will be based on which provided the best balance. Propensity score methods that estimate the average treatment effect on the treated will be calculated and will be compared on the basis of covariate balance as measured by the absolute standardized difference (ASD), which is the difference in means or proportions expressed in pooled standard deviation units. We will compare the approaches on the basis of the number of variables with an ASD of >0.10 and the mean ASD, and the weighting approach with the fewest number of variables with covariate imbalance will be selected for analysis. If two methods achieve the same minimum number of variables with covariate imbalance, the method with the smallest ASD across all variables will be selected for outcome analysis. Notably, one data analyst will balance the data without access to the outcome data and a separate individual will perform the outcome analysis using the balanced data, thus removing the potential for bias resulting from repeated applications of covariate balancing to obtain a desired study outcome.

In the final PSW cohorts, covariate balanced cumulative incidences and 95% CI will be calculated for all device cohorts. A weighted (covariate balance weights) log-binomial regression outcome will be used with treatment as the only explanatory variable to estimate the covariate balanced RR (target group versus the comparator group for the study outcome of interest). A cluster robust standard error approach will be applied to calculate the variability in the estimate and to construct two-sided 95% confidence intervals. All variables included in the propensity score model are prespecified confounders of the relationship between the circular stapler and AL. If any of those variable don't balance well through propensity scores, it will be added as a covariate in the log-binomial regression model.

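### When a covariate stays unbalanced after weighting, section 6.9.2 corrects the risk ratio but not the comparator incidence printed beside it

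*Supplement*

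**What the plan says.** All of this is in protocol section 6.9.2.

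- **Who is weighted.** "The weighting will be carried out for the comparator group to make it comparable in propensity score to the target group". This targets the average effect in the treated (ATT).
- **Incidences.** "In the final PSW cohorts, covariate balanced cumulative incidences and 95% CI will be calculated for all device cohorts". No covariate step is attached to them.
- **Risk ratio.** A weighted "log-binomial regression outcome will be used with treatment as the only explanatory variable to estimate the covariate balanced RR", with cluster-robust standard errors.
- **Residual imbalance.** A propensity-score variable that does not balance adequately is handled in one way: "it will be added as a covariate in the log-binomial regression model". The section regards all these variables as prespecified confounders. It gives no number for this trigger. The ASD cut-off appears only in the choice of weighting method, which compares "the number of variables with an ASD of >0.10 and the mean ASD".

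The mock-up Tables B-7 and B-8 put cumulative incidence and risk ratio in adjacent columns, in rows for before and after weighting. Section 6.9.3 repeats all primary analyses in the two diverting-stoma strata, and Tables C-9 to C-12 have the same layout.

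**The concern.** Once the imbalance rule is applied, the two columns rest on different adjustments. The RR is adjusted for weights plus the added covariate. The comparator incidence is adjusted for weights alone, although the analyst has just recorded that the weights did not balance a variable the plan calls a confounder. A reader who divides one incidence by the other gets a different RR from the one printed. A reader who wants the absolute difference in leak risk has only the uncorrected incidences to use.

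**Working it through.** **Inputs from the protocol.** Section 6.8 says the comparator's leak risk "ranges from 2% to 3.5% in the literature". Table 2 uses 2% and 3%, RR 1.5, 2 and 2.5, and 6,000 target against 500 comparator patients. The target risk is therefore at most 2.5 × 3% = 7.5% in Table 2, or 2.5 × 3.5% = 8.75% at the top of the cited range.

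**Assumed, because the protocol does not give them.** Covariate prevalence, the covariate's risk ratio for leak, the spread of the weights, and the size of a stoma stratum.

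**Check of the plan's own figures.** A two-proportion test (pooled variance under the null, one-sided 0.025) at 3% and RR 2:
- pooled risk = (15 + 360)/6,500 = 0.0577
- null SE = √[0.0577 × 0.9423 × (1/500 + 1/6,000)] = 0.01085
- alternative SE = √(0.03 × 0.97/500 + 0.06 × 0.94/6,000) = 0.00822
- power = Φ[(0.03 − 1.96 × 0.01085)/0.00822] = Φ(1.06) = 0.856, as printed

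All six rows of Table 2 reproduce to three decimals, so the risks and sample sizes are used as they stand.

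**Step 1, formula.** Let a binary covariate have prevalence p in the weighted comparator and q in the target, and multiply leak risk by k. With no device-by-covariate interaction,

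ratio of printed incidences ÷ adjusted RR = [1 + q(k − 1)] / [1 + p(k − 1)].

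**Step 2, one case.** Take comparator incidence 3.00%, true RR 2, p = 0.30, q = 0.395 and k = 2. The ASD is 0.095/√[(0.30 × 0.70 + 0.395 × 0.605)/2] = 0.20.
- Factor: 1.395/1.30 = 1.073.
- Comparator standardised to the target mix: 3.00% × 1.073 = 3.22%.
- Target: 2 × 3.22% = 6.44%.
- The tables would print 3.00% and 6.44% (ratio 2.15) beside an adjusted RR of 2.00. Standardised incidences would be 3.22% and 6.44% (ratio 2.00).

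**Step 3, range (p = 0.30).**

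| Residual ASD | q | k = 1.5 | k = 2 | k = 2.5 |
|---|---|---|---|---|
| 0.10 | 0.347 | 1.020 | 1.036 | 1.049 |
| 0.20 | 0.395 | 1.041 | 1.073 | 1.098 |

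With p = 0.20 the lowest value is 1.019, so the mismatch is about 2% to 10%. It reverses if the covariate is commoner in the comparator. The more extreme assumption of ASD 0.30 and k = 3 gives 1.886/1.60 = 1.179.

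**Step 4, simulation.** In 300 data sets of the step 2 type, mean comparator incidence was 3.08% weighted and 3.30% standardised (3.30/3.08 = 1.071). With three such covariates at k = 1.5 it was 2.96% and 3.34% (1.128, against 1.041³ = 1.128), so imbalances in the same direction compound.

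**Step 5, does the covariate-adjusted log-binomial model fit?** With device alone it is saturated and safe. Failure means non-convergence or a fitted risk reaching 1.
- 6,000 against 500, one to four added binary covariates (k = 1.5 to 2): 0%.
- Same sizes, larger ordinary sets, including multi-level factors with up to 13 terms: 0% to 2.5%.
- Assumed stratum of 1,200 against 100: 0% to 5.5% with three or four covariates, 1% to 4% with 7 terms, 5% to 8% with 10, and 7% to 23% with 12 to 13.
- 12 terms with a 2.5-fold level in each of four variables: 0% to 20% at risk and RR pairs from Table 2, and 70% at 3.5% with RR 2.5. Where log-binomial failed in these cells, weighted Poisson converged but gave fitted risks above 1 in 3% to 45% of data sets.

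**The case against.** The trigger is narrow: a covariate enters only if imbalance survives the better of two weighting methods. Primary objectives 2 and 3 are relative risks, and the rule does correct those. Section 6.9.1.2 makes the incidences for objective 1 unadjusted, so the weighted incidences are supporting output. The table rows are accurately labelled as after weighting, and Tables B-4 and B-5 show the residual ASDs. The shift is also small against sampling error. At 3%, 500 comparators yield about 15 events, and exp(1.96/√15) = 1.66, so the confidence limits span a factor of roughly 1.7 either way even before weighting widens them. A footnote could explain that the RR need not equal the ratio of the incidences.

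Most of this stands, and it limits the point to a modest one. It does not remove it. Section 6.9.2 describes these incidences as covariate balanced, the error is systematic, and the model already fitted contains what is needed to correct it.

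A reader might infer more from the imbalance rule: that the log-binomial model is likely to break down at this study's leak risks. The documents do not support that. At 2% to 3.5% in the comparator and RR up to 2.5, failure in the full cohort was rare in ordinary cases. It became frequent only under strong assumed covariate sets or with many terms in a small assumed stratum. A fallback for non-convergence is also detail commonly left to an analysis plan, and no separate one is shown, so its absence is not a fault in itself.

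**Conclusion.** The point holds for the incidences. When the imbalance rule is applied, the comparator's weighted incidence keeps the residual confounding and disagrees with the adjusted RR beside it, by about 2% to 10% for one covariate with ASD 0.10 to 0.20 and risk ratio 1.5 to 2.5. That size rests on assumed prevalences of 0.20 to 0.30 and assumed covariate strengths. It also reads the unquantified trigger as an ASD above 0.10.

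Two stronger readings should be avoided. The incidences are not confounded in both cohorts: only the comparator is weighted, so without trimming the target's value is simply its observed incidence. Nor does this bias the primary RR, which receives the correction. Convergence is a secondary matter, relevant mainly with many added terms or in the small stoma strata.

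**What to change.** Add to section 6.9.2: whenever a covariate enters the outcome model, predict each target patient's risk from that weighted model under each device, average over the target group, and report the two averages as the covariate-balanced incidences. Take the RR as their ratio, with confidence intervals from the same cluster-robust procedure. With a log link and no device-by-covariate interaction, this ratio equals the model's device RR, so the planned RR is unchanged and the two columns agree. Apply the same rule to Tables C-9 to C-12.

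As a secondary safeguard, name weighted Poisson regression (log link, robust variance) for use if the covariate-adjusted log-binomial fit does not converge. It gives the identical RR when device is the only term. Its drawback is that fitted risks can exceed 1 in extreme cases, so the largest fitted risk should be checked before standardising.

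The cost is a few sentences and a few lines of code. No result changes if every covariate balances.

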6.9.3 Secondary analysis

In the secondary analyses, all primary analyses will be repeated separately in those with and without a diverting stoma procedure prior to or on the same day as the index procedure (i.e., left-sided colorectal surgery) during the index admission. See the expected outputs from [Table C- 1](#) and [Table C- 12](#).

6.9.4 Sensitivity analysis

PHD is not a longitudinal patient database; rather, it is a longitudinal hospital database for the duration of continuous participation for each institution. The treatment pathway for each patient is not fully observed. Patients who receive care at another hospital after the index procedure, even within PHD, will be represented as a new patient. To minimize the potential impact of misclassification of study outcome resulting from the loss of follow-up, a sensitivity analysis will be conducted by repeating the primary analysis among patients from hospitals

RWE23-SAF-001:Comparative safety study to assess the risk of AL of 2-row vs 3-row circular staplers

with at least 30 days continuous enrollment in PHD after the patients' index procedure. See the expected outputs in [Table B- 7](#), [Table B- 8](#), [Table C- 9](#), [Table C- 10](#), [Table C- 11](#), and [Table C- 12](#).

7 QUALITY CONTROL

The study will be completed per the quality control guidance outlined in the Epidemiology, Medical Devices: Protocol Driven Research Study Checklist and its associated documents.

8 LIMITATIONS OF RESEARCH METHODS

The study is observational in nature and thus susceptible to limitations.

The first relates to the validity of the diagnosis of anastomotic leak. As with any other non-interventional database study using health insurance administrative claims or electronic health records (EHR), identification of medical events, such as anastomotic leak or co-morbidities, is limited to data that are captured as part of the medical record or claims, which are not primarily collected for research purposes, and will rely on appropriate diagnostic codes to detect these events. As there is no specific diagnosis code for anastomotic leak in the ICD-10-CM taxonomy, the anastomotic leak surrogate diagnoses, such as abscess of intestine, fistula of intestine, peritonitis, or peritoneal abscess, will be used to define AL in the PHD. Misclassification bias can result if study patients are not categorized correctly with regards to outcome, however, should be non-differential between the comparison groups.

Misclassifications due to the secondary use of billing data may also lead to under or overestimation of cohort size. For example, the search strategy designed in this study may underestimate the prevalence of products in the database if the search strategy missed any incorrectly coded entries for study devices such as misspellings leading to misclassification of the exposure. However, there is no evidence that the misclassification bias would be differential between the comparison groups.

Indication for product usage is not specifically stated in the PHD; it is being inferred based on the primary procedure codes recorded during the index hospitalization. Therefore, misclassification of indication in this study is possible but should be non-differential between the comparison groups.

Furthermore, PHD is not a longitudinal patient database; rather, it is a longitudinal hospital database for the duration of continuous participation for each institution. The treatment pathway for each patient is not fully observed. Patient records within a given institution are linked such that additional care at the same institution as the index procedure will be attributed to the same patient. However, patients who receive care at another hospital, even within PHD, will be represented as a new patient. This limitation may lead to underestimation of AL that occurred after the discharge from the index admission. To minimize the potential impact of misclassification of study outcome resulting from such loss of follow-up, a sensitivity analysis will be conducted by repeating our primary analysis among patients from hospitals with at least 30-day continuous enrollment in PHD after the patients' index procedure.

RWE23-SAF-001:Comparative safety study to assess the risk of AL of 2-row vs 3-row circular staplers

Finally, PHD represents data from hospitals that are part of the Premier healthcare performance improvement alliance of approximately 1,041 US hospitals from around the US but are not a random selection of US hospitals and under-represents hospital outpatient procedures. Although the database represents all regions and most payers, this characteristic of the database may affect the generalizability of the study results.

9 PROTECTION OF HUMAN SUBJECTS

This study will utilize a secondary source of de-identified data, the PHD.

The use of PHD was reviewed by the New England Institutional Review Board (IRB) and was determined to be exempt from broad IRB approval, as this research project did not involve human subjects research.

The PHD consists of de-identified healthcare records. In the US, retrospective analyses of the PHD data are considered exempt from informed consent and institutional review board (IRB) approval as dictated by Title 45 Code of Federal Regulations, Part 46 of the United States, specifically 45 CFR 46.101(b)(4).

Confidentiality of patient records will be maintained at all times. All study reports will contain aggregate data only and will not identify individual patients or physicians. At no time during the study will patients be requested with identifiable information, except when required by law.

10 MANAGEMENT AND REPORTING OF ADVERSE EVENTS AND ADVERSE REACTIONS

In this study, potential product complaints or safety signals may be identified. Thus, any potential combinations of specific product brand and safety outcomes will be reported to the operating company complaint handling unit (CHU) upon internal approval of the study report or manuscript or J&J receipt of the external data report. For all events that may be deemed product complaints, the data captured in the final study report, manuscript, or external report will constitute all clinical information known regarding these product complaints/adverse events. No follow-up on these potential adverse events or complaints can be conducted. The operating companies CHU is responsible for determining if they are actual product complaints and/or product-related adverse events. Communication of all potential Product Complaints to the appropriate operating company CHU must be done within 48 hours of internal approval of the final study report or manuscript or J&J receipt of an external study report using the Database RRA Potential Complaint Forwarding Form (100915839).

NOTE: For these studies, the date the final study report is approved, or the date the manuscript is internally approved, or the J&J receipt date for an external study report shall be considered the awareness date for the CHU.

11 DISSEMINATION PLAN

A final report will be created from study results and will be submitted for publication in a peer reviewed journal according to the J&J Publication Policy.

APPENDIX A: DIAGOSIS AND PROCEDURE CODES

Table A- 1: Procedure Codes (ICD-10-PCS) for Left-sided Colorectal Surgery

CODE	CODE DESCRIPTION
ODTG%	Resection, large intestine, left
ODTM%	Resection, Descending Colon
ODTN%	Resection, Sigmoid Colon
ODTP%	Resection, Rectum
ODBG%	Excision, large intestine, left
ODBM%	Excision, Descending Colon
ODBN%	Excision, Sigmoid Colon
ODBP%	Excision, Rectum
ODQM%	Repair, Descending Colon
ODQN%	Repair, Sigmoid Colon
ODQP%	Repair, Rectum

'%' at the end of the code denotes any value for subsequent characters.

'%' in the middle of the code denotes any valid value for a character in that specific position

RWE23-SAF-001:Comparative safety study to assess the risk of AL of 2-row vs 3-row circular staplers

Table A- 2: Diagnosis Codes (ICD-10-CM) Indicating Anastomotic Leak

CODE	CODE DESCRIPTION
K63.2	Fistula of intestine
K65.0	Generalized Peritonitis
K65.1	Peritoneal abscess
K91.89	Other postprocedural complications and disorders of digestive system
Y83.2	Surgical operation with anastomosis, bypass or graft as the cause of abnormal reaction of the patient, or of later complication, without mention of misadventure at the time of the procedure

Table A- 3: Procedure Codes (ICD-10-PCS) for Diverting Stoma

CODE	CODE DESCRIPTION
0D18%%4	Bypass Small Intestine to Cutaneous
0D1B%%4	Bypass Ileum to Cutaneous
0D1E%%4	Bypass large intestine to Cutaneous
0D1H%%4	Bypass Cecum to Cutaneous
0D1K%%4	Bypass Ascending Colon to Cutaneous,
0D1L%%4	Bypass Transverse Colon to Cutaneous
0D1M%%4	Bypass Descending Colon to Cutaneous
0D1N%%4	Bypass Sigmoid Colon to Cutaneous

'%' in the middle of the code denotes any valid value for a character in that specific position

RWE23-SAF-001:Comparative safety study to assess the risk of AL of 2-row vs 3-row circular staplers

Table A- 4: Diagnosis Codes (ICD-10-CM) for Comorbid Conditions

Comorbid conditions	CODE	DESCRIPTION
Alcohol dependency	F10.2%	Alcohol dependence
Cardiovascular diseases	G45%, G46%, I60%, I61%, I62%, I63%, , I65%, I66%, I67%, I68%, I69%, H34.0%	cerebrovascular disease
	I43, I50%, I09.9, I11.0, I13.0, I13.2, I42.0, I42.5, I42.6, I42.7, I42.8, I42.9	congestive heart failure
	I20%, I23%, I24%, I25%	ischemic heart disease
	I21%, I22%	myocardial infarction
	I70%, I71%, I73.1, I73.8%, I73.9, I77.1, Z95.8%, Z95.9	peripheral artery disease
Chronic obstructive pulmonary disease	J44.0, J44.1, J44.9	Chronic obstructive pulmonary disease
Coagulation defects	D65, D66, D67, D68.0, D68.1, D68.2, D68.3%, D68.4, D68.5%, D68.6%, D68.9	Coagulation defects
Diabetes	E11.%, E10.%, E13.%, O24.%, E08.%, Z79.4, Z79.84	Diabetes mellitus, Gestational diabetes, Secondary diabetes, long term (current) use of insulin/oral antidiabetic drugs
Hypertension	I10, I11%, I12%, I13%, I15%	Hypertension
Immunodeficiency/immunosuppression	D80%, D81%, D82%, D83%, D84%	immunodeficiencies
	Z92.25	Personal history of immunosuppression therapy
	Z79.52	Long term (current) use of systemic steroids
	B20	AIDS/HIV
Kidney disease	N18%, N19, I12.0, I13.1%, N03.2, N03.3, N03.4, N03.5, N03.6, N03.7, N05.2, N05.3, N05.4, N05.5, N05.6, N05.7, N25.0, Z49.0%, Z94.0, Z99.2	Renal diseases
Malnutrition	E41, E42, E43, E44%, E46, E63%	Malnutrition, nutritional deficiencies
Obesity	E66.0%, E66.1, E66.2, E66.8, E66.9, Z68.3%, Z68.4%	Obesity, body mass index (BMI) 30-39, BMI 40 or greater

'%' at the end of the code denotes any value for subsequent characters.

RWE23-SAF-001:Comparative safety study to assess the risk of AL of 2-row vs 3-row circular staplers

Table A- 5: Diagnosis Codes (ICD-10-CM) for Indications of Surgery

PRIMARY DIAGNOSIS	CODE	CODE DESCRIPTION
Malignant neoplasms	C18.6	Malignant neoplasm of descending colon
	C18.7	Malignant neoplasm of sigmoid colon
	C18.8	Malignant neoplasm of overlapping sites of colon
	C18.9	Malignant neoplasm of colon, unspecified
	C19	Malignant neoplasm of rectosigmoid junction
	C20	Malignant neoplasm of rectum
Benign neoplasm	D12.4	Benign neoplasm of descending colon
	D12.5	Benign neoplasm of sigmoid colon
	D12.6	Benign neoplasm of colon, unspecified
	D12.7	Benign neoplasm of rectosigmoid junction
	D12.8	Benign neoplasm of rectum
Diverticular disease or Diverticulitis	K57.2%	Diverticulitis of large intestine
	K57.3%	Diverticular disease of large intestine
	K57.8%	Diverticulitis of intestine, part unspecified
	K57.9%	Diverticular disease of intestine, part unspecified
Intestinal obstruction	K56.2	Volvulus
	K56.6%	Other and unspecified intestinal obstruction

'%' at the end of the code denotes any value for subsequent characters.

Table A- 6: Diagnosis Codes (ICD-10-CM) for Conversion of Minimally Invasive Procedure to Open Procedure

CODE	CODE DESCRIPTION
Z53.31	Laparoscopic surgical procedure converted to open procedure
Z53.32	Thoracoscopic surgical procedure converted to open procedure
Z53.33	Arthroscopic surgical procedure converted to open procedure
Z53.39	Other specified procedure converted to open procedure

RWE23-SAF-001:Comparative safety study to assess the risk of AL of 2-row vs 3-row circular staplers

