5.2 Objectives

Among patients who underwent a left-sided colorectal surgery (i.e., the index procedure), such as hemicolectomy, sigmoid colectomy, or rectal resection, in which a study device (Ethicon Manual Circular Staplers, Medtronic EEA™ Circular Stapler with DST Series™ Technology, or Medtronic EEA™ Circular Stapler with Tri-Staple™ Technology) was used:

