6.3 Sample Selection

Inclusion Criteria

Patients who meet all of the following criteria will be included in this study:

- 1) Billing charges for a study device (Ethicon Manual Circular Stapler, Medtronic EEA™ Circular Stapler with DST Series™ Technology, or Medtronic EEA™ Circular Stapler with Tri-Staple™ Technology) between January 1, 2019, and June 30, 2022 (or latest available data)
- 2) Undergoing a left-sided colorectal surgery (i.e., the index procedure), defined as presence of a qualifying procedure code for left-sided colorectal surgery (see [Table A-1](#))
- 3) Aged 18 years or older at the index procedure.

Exclusion Criteria

Patients who meet any of the following criteria will be excluded:

- 1) Patient encounters where more than one study device (Ethicon Manual Circular Stapler, Medtronic EEA™ Circular Stapler with DST Series™ Technology, or Medtronic EEA™ Circular Stapler with Tri-Staple™ Technology) was used in the same index procedure
- 2) Missing patient age or sex
- 3) Presence of an admission diagnosis indicating anastomotic leak (See ICD-10-CM in the [Table A-2](#)) during the index admission noted as present on admission*

*Present on admission will be identified with “Yes” in the present on admission field in the PHD.

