6.6.2 Procedural Characteristics

- Surgical site (indication for product usage): primary organ involved in the index procedure as defined by the primary procedure code (See [Table A- 1](#)).
 - Rectum
 - Sigmoid
 - Descending colon
 - others
- Primary diagnosis: Primary ICD-10-CM discharge diagnosis code recorded during the index hospital admission will be used to designate indication for surgery (See [Table A- 5](#)).
 - Malignant neoplasms
 - Benign neoplasm

RWE23-SAF-001:Comparative safety study to assess the risk of AL of 2-row vs 3-row circular staplers

- Diverticular disease or Diverticulitis
 - Intestinal obstruction
 - Others
- Diverting stoma (yes, no) occurred prior to or on the same day as the index procedure (i.e., left-sided colorectal surgery) during the index admission: defined as the presence of an ICD-10-PCS procedure code indicating diverting stoma (see [Table A- 3](#)) identified prior to or on the same day as the index procedure during the index admission
 - Surgical approach:
 - Open
 - Laparoscopic
 - Robotic assisted
 - Unknown

Surgical approach is determined by the primary and secondary procedure code. For a *primary* procedure code in ICD-10-PCS, the fifth character of the code explicitly identifies the surgical approach with '0' standing for an open procedure and characters other than '0' representing a laparoscopic approach, unless the presence of a *secondary* procedure code (i.e., ICD-10-PCS: 8E0W%CZ—Robotic Assisted Procedure of Trunk Region) indicating a robotic assistance procedure. Conversions from laparoscopic or unknown surgical approach to open surgical approach will be categorized as open surgery (the procedure code list for conversions is provided in [Table A- 6](#)).

- Year of index procedure
- Admission type during index procedure (elective admission; emergent or urgent admission): elective surgery was scheduled in advance, while urgent or emergency surgery was done because of an urgent medical condition. We assume an index encounter categorized as elective indicates a procedure scheduled in advance, while urgent or emergency index encounter admissions reflect an urgent medical condition.

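### Table A-1 and an admission-level device link can admit patients whose circular stapler was not used for left-sided surgery

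*Supplement*

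**What the plan says.** Section 5.2 describes the population as left-sided colorectal surgery with a study stapler, "such as hemicolectomy, sigmoid colectomy, or rectal resection". Section 6.3 requires both "Billing charges for a study device" (criterion 1) and left-sided surgery, "defined as presence of a qualifying procedure code for left-sided colorectal surgery" (criterion 2, pointing to Table A-1).

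Table A-1 has 11 code families. Besides Resection it has Excision rows such as "Excision, large intestine, left" and Repair rows such as "Repair, Descending Colon". All end in a percent sign, which "at the end of the code denotes any value for subsequent characters". Section 6.6.2 explains that the fifth character carries the approach, with "characters other than '0' representing a laparoscopic approach" unless a robotic code is present. No approach is excluded.

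Section 6.2 defines the index procedure through use of the study device. Table B-1 asks only that the left-sided surgery and the device charge belong to one admission.

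**The concern.** A device charge and a left-sided code in one stay need not belong to the same operation. If the stapler was used elsewhere, and the left-sided code records an incidental repair or a small excision, the patient has no left-sided stapled anastomosis that could leak. Such a patient still counts in the denominator. The patient can also count as an event, because Section 6.5 accepts peritonitis, abscess, fistula or a stoma on days 1 to 30 without evidence of an anastomosis.

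The later steps do not clearly remove these patients. The propensity model in Section 6.9.2 has surgical site, diagnosis, approach and admission type, but not procedure type (resection, excision or repair). The only sensitivity analysis (Section 6.9.4) concerns hospital enrolment. Section 8 says that misclassified indication should be non-differential, without a check.

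**Working it through.** **1. What qualifies.** Table A-1: 4 Resection + 4 Excision + 3 Repair = 11 families. Seven of the 11 are not Resection, and each leaves every character after the fourth open.

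**2. Trace one patient.** An adult has one study stapler charged for a non-left-sided operation and a sigmoid repair code in the same stay.
- Criterion 1 (device charge): met.
- Criterion 2 (any Table A-1 code): met.
- Criterion 3 (age): met.
- Exclusions (two study devices, missing age or sex, leak code present on admission): none applies.
- Table B-1 link (same admission): met.

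Section 6.2 would look for the procedure that used the device, but the visible text has no rule matching the charge to a dated procedure code.

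**3. Pool by arm (Section 6.8).** Share of device users without left-sided surgery:
- Ethicon: 1 − 6,000/10,000 = 40% (the base is given as more than 10,000)
- DST: 1 − 6,000/13,000 = 54%
- Tri-Staple: (623 − 526)/623 = 97/623 = 16%

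These are patients whom criterion 2 should remove. They show where incidental codes could arise, not how many did.

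**4. Reproduce the plan's power, then illustrate.** Table 2, row RR 2 and risk 3%, with 500 versus 6,000 patients and one-sided 0.025. Using the pooled two-proportion normal approximation:
- pooled risk = (15 + 360)/6,500 = 0.0577
- null SE = √[0.0577 × 0.9423 × (1/500 + 1/6,000)] = 0.01085
- alternative SE = √(0.03 × 0.97/500 + 0.06 × 0.94/6,000) = 0.00822
- power = Φ[(0.03 − 1.96 × 0.01085)/0.00822] = Φ(1.06) = 0.856, as printed. The other five rows also reproduce.

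Now let f be the share of patients without the target anastomosis (equal in both arms) and b their rate of surrogate codes. Both are assumptions. Observed risk = (1 − f) × p + f × b.

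| f | b | Observed RR (true 2) | Power if kept | Power if removed |
|---|---|---|---|---|
| 0 | – | 2.00 | 0.856 | 0.856 |
| 10% | 0 | 2.00 | 0.806 | 0.809 |
| 10% | 5% | 1.84 | 0.756 | 0.809 |
| 20% | 5% | 1.71 | 0.636 | 0.751 |
| 20% | 10% | 1.55 | 0.554 | 0.751 |

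Example for row 3: (0.9 × 0.06 + 0.1 × 0.05)/(0.9 × 0.03 + 0.1 × 0.05) = 0.059/0.032 = 1.84.

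**5. Direction when shares differ.** Take a true RR of 1 and a 3% risk.
- 10% in the target arm only, b = 0: (0.9 × 0.03)/0.03 = 0.90.
- 10% in the target arm only, b = 5%: (0.027 + 0.005)/0.03 = 1.07.
- 10% in the comparator only, b = 0: 1/0.9 = 1.11.

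The sign depends on which arm holds more such patients and on whether b lies below or above the true leak risk. The documents settle neither.

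**6. Sensitivity of the small arm.** 526 × 2% = 10.5 events and 526 × 3% = 15.8 events. One event gained or lost moves the unweighted comparator risk by 1/15.8 = 6% to 1/10.5 = 10%.

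**The case against.** The strongest reply is the device gate. All criteria must be met, so a repair or biopsy in a stay with no study-stapler charge never enters. Section 4 describes circular staplers as anastomosis devices, so most included patients probably do have an anastomosis. This stands. It leaves only the route in which charge and code come from different procedures in one stay.

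Four stronger readings are tempting and are not supported:
- *The code list contradicts the objective.* Section 5.2 gives resections as examples and does not mention anastomosis. The breadth of Table A-1 is a design choice. Excision is also legitimate in itself; the weakness is its open trailing characters.
- *The wildcard demonstrably admits biopsies.* The documents show only that every trailing value is accepted. They do not print the qualifier values.
- *An early biopsy code could set the index date, so that a later planned stoma counts as a leak.* Section 6.2 ties the index to the procedure that used the device. A stoma made at that operation falls on the index day, where Section 6.6.2 makes it a baseline covariate.
- *The unequal pools push the relative risk one way.* Step 5 shows that they do not fix the direction.

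Partial handling also deserves credit. Site, diagnosis and approach are weighted, and Table B-6 shows incidence by each. The site class for other organs may gather some of these patients. It does not isolate them, because the left large intestine rows have no site class of their own either.

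**Conclusion.** The gap is real but narrow. As written, the cohort rules can admit patients whose stapler was not used for left-sided surgery, and no planned analysis shows their effect. The pools from which they could come are unequal (about 40%, 54% and 16%). Their number, and the size and direction of any bias in the relative risk, cannot be obtained from the documents. The shares and background rates in the working are illustrations, and the power figures ignore weighting and clustering.

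The conclusion rests on the visible text. Section 6.4 has redacted bullets; if they already match the charge to the procedure date, that part of the point is met. The change is worth making because it is cheap and brings the cohort closer to the stated population.

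**What to change.** 1. In Section 6.3 and Table B-1, require the study-stapler charge to carry the same service date as the qualifying Table A-1 code, and keep the device-based index of Section 6.2. Section 6.1 says that billed items are date-stamped, so this can be done.
2. Restrict the Excision rows to therapeutic (non-diagnostic) codes with an operative approach, and list the accepted trailing characters.
3. Do not let a Repair code qualify on its own in the primary cohort. Add repair-only patients back in a sensitivity analysis.
4. Show in Table B-1 how many patients each rule removes, by device. This supplies the count that is now missing.

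Cost: an appendix edit, one added analysis and a re-run of the cohort query. Cohorts shrink slightly, including the comparator of about 526. Some true anastomoses coded only as repair may leave the primary cohort; the sensitivity analysis recovers them. A same-day incidental therapeutic excision could still qualify, so the rules narrow the route without closing it completely.
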